# 11.0 TOXICITIES/SIDE EFFECTS

During radiation, adverse events will be graded using the NCI Common Terminology Criteria for Adverse Events—Version 4.0. A copy of the CTCAE version 4.0 can be downloaded from the CTEP home page (http://ctep.info.nih.gov).

Treatment modifications are based on CTCAE version 4.0. Once a patient has had a doxorubicin dose reduction for toxicity, the dose will not be re-escalated.

Reproductive risks: There is a risk of birth defects associated with this study. Patients must use birth control while on this study. Women should not breastfeed while on this study.

#### 11.1 Radiation Therapy-Associated Adverse Events

Reversible radioepithelitis of pharyngeal mucosa is expected and its timing with dose and severity will be noted and graded according to NCI CTCAE v4.0. Epilation of treated areas and various degrees of skin reaction are expected. Other expected acute reactions include hypogeusia, dysphagia, thick saliva, hoarseness, radiation dermatitis, nausea, vomiting, anemia, fatigue, and weight loss.

Late toxicities are those that occur at least 3 to 4 months post radiation. Late effects may include permanent xerostomia, hypogeusia, dysphagia, ototoxicity, nasal dryness, serous otitis media, dental decay, hypothyroidism, dysphagia, and trismus. Osteoradionecrosis may occur in 5% or less of patients, but can be reduced by dental evaluation before radiation.

#### 11.2 Chemoradiation Therapy-Associated Adverse Events

The following may be experienced with doxorubicin: myelosuppression, decreased albumin, decreased calcium, abnormal liver function tests, kidney problems, digestive, or pancreas problems, high blood sugar, nausea, vomiting, loss of appetite, heartburn, hair loss, fatigue, skin rash, diarrhea, belly pain, weight loss. In rare instances, heart damage manifested as congestive heart failure may occur.

Previous data have noted that the additional of concurrent chemotherapy only resulted in a 10% increase in acute grade 3 hoarseness, but with no difference in late toxicity with a

median follow up of 35 months. There were no differences in acute or late toxicities for dermatitis, dysphagia, mucositis, nausea, vomiting, fatigue, or need for a feeding tube. Chemotherapy will be held for ANC < 1, platelets < 75,000. Dose adjustments for intolerable Grade 2 or Grade 3-4 toxicities associated with the chemotherapy will be up to the treating physician.

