# **10.1 EVALUATION DURING TREATMENT/INTERVENTION**

## **10.1 Evaluation during IMRT**

Patients will be assessed at weekly status check as per institutional standard practice. At the weekly assessments patients will have a limited physical exam, KPS evaluation, and toxicity assessments. CBC will also be completed weekly during treatment. A recommended DW and multiparametric MRI should also take place approximately weekly unless contraindicated for patients.

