Confirmation of Non- Anaplastic Non-Medullary Thyroid Cancer a	Х		
Collection of tumor tissue for translational research if available a	Х		
H & P by MD	Х	Xp	Х
KPS	Х	Х	Х
CBC	Х	Х	
Comprehensive Metabolic Panel	Х		
TSH, Thyroglobulin, T3, T4	Х		
EKG	Xc		
Recommended CT and/or MRI of the neck with contrast	X		Xď
Recommended DW and multiparametric MRI unless contraindicated for patients	Xc	Х	Xď
FDG PET/CT	Xc		
Pregnancy Test (for women of child bearing potential)	Xe		
Speech and Swallowing Evaluation	Х		Xţ
Dental Evaluation (unless patient is edentulous)	Xc		Xa
Low dose radiosensitizing doxorubicin (10 mg/m  )		Х	

IMRT		X h	
AE monitoring i		Х	Х
Co-morbidities	Х		

- a) Any time prior to RT start
- b) Weekly status check
- c) Within 8 weeks of RT start
- d) At 3 months (+/- 4 weeks) and 6 months (+/- 4 weeks), and then every 6 months (+/- 8 weeks) until 2 years
- e) Within 14 days of RT start
- f) Performed after radiation at approximately 6 months, 12 months, 18 months, and 24 months post-treatment.
- g) At approximately 4-8 months post-RT only
- h) Daily except for weekends and holidays
- i) AEs will be assessed according to CTCAE v 4.0 throughout the treatment course and in follow up.
- j) Pre-treatment MRI to be completed within 8 weeks prior to treatment start, if recommended

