## **14.0 BIOSTATISTICS**

The primary objective of this study is to determine the 2-year loco-regional progression-free rate. Current literature showed that the 2-year loco-regional progression-free rate is about 40% [16-24]. We expect to improve this rate substantially to 90% by applying the proposed chemoradiation treatment strategy. It should be mentioned that according to previous versions of the protocol 8 patients had been treated with IMRT alone. But prospectively we will treat patients with the current standard which is chemoradiation. To this end we will still employ a single-stage binomial design. We will recruit 19 patients, and we will claim the proposed treatment promising when at least 14 patients are without progression of disease at 2 years from the end of the treatment. This decision rule gives a power (that is, probability of declaring success when the true 2-year progression rate is 90% or higher) of 0.99 with the

type 1 error rate (that is, probability of declaring success when the true 2-year progression rate is 40% or lower) less than 0.01. Patients who died due to any reason, or were lost to F/U within 2 years will be regarded as having loco-regional progression. Patients who do not complete treatment due to excessive toxicity will be excluded from the primary endpoint analysis and replaced by new eligible patients. We expect to accrue the total of 19 analyzable patients in 2 years. The 8 patients who had received IMRT alone will not be counted towards this endpoint and will be summarized separately.

To better understand the loco-regional progression we will also use the cumulative incidence function for summaring the endpoint of time to loco-regional failure, which will be carried out by a competing risks anlaysis. Overall survival rates will be assessed by Kaplan-Meier method. Rates of (acute or late) toxicities will be computed by sample proportions and confidence intervals will also be provided. Summary statistics and/or longitudinal plots for the Modified Barium Swallow-Imp and Penetration-Aspiration scales will be supplied for assessing objective measures of late dysphagia. BRAF and other mutation measurements at baseline will be correlated with clinical outcomes such as overall survival and local-regional control using survival analysis tools. All secondary endpoints will be analyzed for the 19 patients under chemoradiation. The 8 patients who had received IMRT alone will be summarized separately.

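### Section 11 names toxicities that need a blood chemistry value, but none is scheduled after baseline, so proportions over 19 would be biased downward by an unknown amount

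*Combined protocol and SAP*

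**What the plan says.** Section 11.2 gives the possible effects of doxorubicin, among them "myelosuppression, decreased albumin, decreased calcium, abnormal liver function tests, kidney problems, digestive, or pancreas problems, high blood sugar". Section 11.1 places hypothyroidism among the late effects of radiation ("dental decay, hypothyroidism, dysphagia, and trismus").

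In the schedule table at the end of Section 10.2, the rows "Comprehensive Metabolic Panel" and "TSH, Thyroglobulin, T3, T4" each carry one mark, in the pre-treatment column. Section 8 agrees: its chemistry and thyroid tests all fall within 30 or 14 days before treatment. For the treatment period Section 10.1 says "CBC will also be completed weekly during treatment", and the chemotherapy part of Section 9 asks for a blood count in the 48 hours before each dose. Section 10.2.1 requires examination, performance status and toxicity grading at follow-up visits, and no laboratory test.

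Section 11.0 states "Treatment modifications are based on CTCAE version 4.0". Section 14 states "Rates of (acute or late) toxicities will be computed by sample proportions and confidence intervals will also be provided", and it analyses all secondary endpoints in the 19 patients given chemoradiation. Acute and late toxicity rates are secondary objectives (2.2.2 and 2.2.3), and Section 1.0 gives prospective capture of toxicity as the purpose of the protocol.

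**The concern.** Low albumin, low calcium, abnormal liver tests and raised glucose are recognised from a blood value. So is a kidney abnormality without symptoms. Toxicity grading at a visit cannot supply a grade for these if no sample was taken. The schedule requires no such sample after baseline, yet the analysis fixes the denominator at 19 and does not say how an untested patient is handled.

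If untested patients stay in the denominator, the proportion mixes two things: patients shown to be free of the toxicity, and patients in whom nobody looked. The confidence interval covers sampling error only, so a reader could take a low figure with a tidy interval as evidence of safety. That bears on a stated purpose of the study. The primary endpoint is not affected.

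**Working it through.** The documents give no rate for any laboratory toxicity, so there is no stated figure to reproduce. The check is a comparison of sections, followed by arithmetic for scale.

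**Step 1: named toxicity against required test.**

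| Named in Section 11 | Before treatment | During treatment | Follow-up |
|---|---|---|---|
| Myelosuppression (11.2) | Blood count | Blood count, weekly and before each dose | None |
| Albumin, calcium, liver, kidney, glucose (11.2) | Chemistry panel | None | None |
| Hypothyroidism (11.1) | TSH, T3, T4 | None | None |

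The holding rule in 11.2 uses neutrophils and platelets, which the required blood count supplies. No required test supplies a value for the chemistry row.

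**Step 2: the extreme of no testing.** With n = 19 and no detected case, the two-sided 95% exact upper limit is 1 − 0.025^(1/19) = 0.176. The report would read 0/19 (0% to 17.6%) whatever the true rate.

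**Step 3: partial detection.** Let t be the true rate and d the share of cases that routine care detects. Both are assumptions. The expected observed rate over 19 is t × d, and the chance of reporting 0/19 is (1 − t × d)^19.

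| t (expected true cases, 19 × t) | d | Observed rate t × d | Chance of 0/19 |
|---|---|---|---|
| 10% (1.9) | 10% | 1% | 0.83 |
| 10% (1.9) | 50% | 5% | 0.38 |
| 10% (1.9) | 75% | 7.5% | 0.23 |
| 20% (3.8) | 10% | 2% | 0.68 |
| 20% (3.8) | 50% | 10% | 0.14 |
| 20% (3.8) | 75% | 15% | 0.05 |
| 30% (5.7) | 10% | 3% | 0.56 |
| 30% (5.7) | 50% | 15% | 0.05 |
| 30% (5.7) | 75% | 22.5% | 0.01 |

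The observed rate is below t in every row. How far below depends on d, which the documents do not allow one to estimate. Each missed case moves a proportion by 1/19 = 5.3 percentage points.

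**Step 4: what the denominator does to the interval.** Suppose, for illustration only, that 10 of the 19 had a post-baseline value and none was abnormal. Over those tested the upper limit is 1 − 0.025^(1/10) = 0.308, against 0.176 over 19. The narrower interval credits nine untested patients as event-free.

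**The case against.** The strongest reply is that an empty schedule cell does not mean the test is not done. The study runs within standard care, Section 5.2 gives chemotherapy under institutional guidelines that are not reproduced, and Section 17.4 counts routine blood tests among patient costs. Toxicity is graded throughout treatment and follow-up. The table is also visibly incomplete: it marks FDG PET/CT only before treatment, although Section 10.2.2 requires a scan at three months. Some TSH testing is likely, because Section 3.0 names TSH suppression as standard treatment.

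Much of this stands, and it rules out several stronger readings:

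- A reader might infer that these toxicities would go largely undetected and be reported at near zero. That needs almost no testing outside the schedule, which the documents do not say. With half of cases detected, a 30% rate appears as 15%.
- A reader might infer that an asymptomatic chemistry abnormality could never lead to a dose adjustment. Section 11.2 does not confine adjustment to scheduled tests and leaves it to the treating physician, so a clinically ordered value can prompt it. What holds is that no required test supports it.
- A reader might infer that an unmeasured toxicity is counted as absent by rule. Section 14 is silent. That is the natural result of a fixed denominator of 19, not a stated imputation.

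Hypothyroidism is the weaker example. Some patients enter after surgery and TSH may be deliberately suppressed, so a later TSH value would not by itself show a radiation effect.

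The reply does not close the gap. No section says which routine tests are done, when, or that their results will be collected. The text of Sections 9 and 10 agrees with the table on the absence of scheduled chemistry, so the finding does not rest on blank cells alone. Testing prompted by clinical suspicion is also selective.

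**Conclusion.** The point holds in a limited form. No chemistry or thyroid value is scheduled after baseline for toxicities that Section 11 names, and Section 14 analyses toxicity proportions in a fixed group of 19. If the plan is followed as written, the proportions for laboratory-defined toxicities are biased downward by an amount that cannot be estimated from the documents, and the intervals do not reflect it. The 0/19 result with its 17.6% limit is the worst case, not a forecast. The true rates (10% to 30%) and detection shares used above are assumptions that show the range.

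The conclusion is firm for albumin, calcium, liver, kidney and glucose, and weaker for hypothyroidism. It concerns descriptive secondary endpoints, but these serve a stated purpose of the protocol, so the plan should be changed.

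**What to change.** 1. Reconcile the assessment schedule (Sections 10.1 and 10.2 and the table) with the toxicities named in 11.1 and 11.2 and with objectives 2.2.2 and 2.2.3. State when post-baseline chemistry values are collected, for example at the existing weekly blood draw, and that chemistry and thyroid results from routine care will be abstracted. Frequency and clinical use are for the investigators to set.
2. In Section 14, for each laboratory toxicity, report as denominator the number of patients with at least one post-baseline value, alongside the count over 19. List the others as not assessed, not as event-free. Note that clinically triggered testing is selective, so the proportion among those tested may err upward where the proportion over 19 errs downward.
3. Interpret hypothyroidism against baseline surgical and TSH-suppression status.

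The cost is a schedule amendment, a little extra collection and the abstraction of routine results. The denominator rule needs no new procedure. Reported rates may look less favourable.

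A separate tidying point: the 14-day panel in Section 8 includes magnesium and coagulation tests that the table does not show, and the two should be reconciled.

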# 12.0 CRITERIA FOR THERAPEUTIC RESPONSE/OUTCOME ASSESSMENT

The primary endpoint of this study is to assess the 2-year loco-regional progression-free interval using standard post-radiation imaging studies. Scans will be performed at 3 months (+/- 4 weeks) and 6 months (+/- 4 weeks) post-RT and then every 6 months (+/- 6 weeks) until 2 years post-RT. Patients will be followed for life with standard screening for disease recurrence, according to the schedule in Sections 9 and 10.Patients will be classified as loco-regional progression free as long as there is no evidence of loco-regional progression of disease. Loco-regional failure will be defined as infield progression if included in the RT field and meets one of the following criteria: 25% increase in tumor volume, new lesions, and/or 25% increase in metabolic tumor volume or total lesion glycolysis.

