### 10.2 Follow-up after IMRT

**10.2.1** Clinic visits will take place approximately every 3 months for 2 years, approximately every 6 months for the next 3 years, and approximately annually thereafter with Radiation Oncology and/or Medical Oncology. This schedule may be altered, as clinically indicated.

Patients who are removed from study for toxicity (but who maintain active follow-up) will be followed according to the same post-treatment surveillance plan as patients who complete study treatment. The following will be completed at these visits: physical exam, KPS assessment, toxicity assessment (according to NCI CTCAE v 4.0)

**10.2.2** Three months (+/- 4 weeks) after completion of IMRT, radiologic assessment will be performed. This will include a diagnostic FDG PET/CT scan, along with a recommended CT and/or MRI scan of the primary tumor/neck, mean and maximum standardized uptake value, metabolic tumor volume, and total lesion glycolysis will be recorded prospectively for all FDG PET/CT scans. The MRI scan may be performed in addition to the CT scan, or instead of the CT scan, as clinically indicated. Imaging will then be repeated at 6 months (+/- 4 weeks) post-RT and then every 6 months (+/- 6 weeks) until 2 years post-RT. The DW and multiparametric MRI will be recommended for 3 months, 6 months, and then every 6 months (all +/- 4 weeks) until 2 years post-RT unless contraindicated for main campus patients only.

**10.2.3** Patients will be advised to undergo routine surveillance dental exams approximately 4 to 8 months after completion of definitive locoregional therapy. The dental visit dates may vary due to logistical considerations, but all patients will be advised to maintain dental follow up. Assessments of salivary flow may be performed at dental visits, but are not mandatory. Additional dental evaluations may be performed, as clinically indicated.

**10.2.4** Mandatory post-treatment evaluation in the Speech and Swallowing Center with Standard objective measures of pre-treatment swallow evaluation using Modified Barium Swallow Imp and Penetration-Aspiration scale. **(See Appendix 1).** Speech and Swallowing assessment should be performed at baseline, and after radiation at approximately 6 months, 12 months, 18 months, and 24 months post treatment.

	Pre-Rx (w ithin 30 days prior to RT unless otherw ise indicated)	Weekly during RT	Follow up (Q3 mos until 2yrs, Q 6 mos until 5yrs; annually thereafter)

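### Progression-free is the default status and no rule covers a missing 2-year scan, so, read literally, an attending but unscanned patient counts toward the 14 of 19

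*Combined protocol and SAP*

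**What the plan says.** **Scoring.** Section 12 bases the primary endpoint on standard imaging after radiation. In-field failure is a 25% rise in tumor volume, in metabolic tumor volume or in total lesion glycolysis, or new lesions. Patients are "classified as loco-regional progression free as long as there is no evidence of loco-regional progression of disease". No minimum assessment is attached to that status. Section 14 adds: "Patients who died due to any reason, or were lost to F/U within 2 years will be regarded as having loco-regional progression". It does not define loss to follow-up.

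**Imaging.** Section 12 and Section 10.2.2 both schedule imaging at 3 and 6 months and then every 6 months to 2 years. At 3 months, Section 10.2.2 includes a diagnostic FDG PET/CT, "along with a recommended CT and/or MRI scan of the primary tumor/neck". For the later time points it names no modality. In the schedule table under Section 10.2, the follow-up neck imaging row reads "Recommended CT and/or MRI of the neck with contrast", the research MRI row is also headed as recommended, and FDG PET/CT is marked before treatment only. The window for the six-monthly scans is +/- 6 weeks in Sections 10.2.2 and 12 but +/- 8 weeks in footnote d of the table.

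**Decision rule.** Section 14 states that "we will still employ a single-stage binomial design", with 19 patients, and calls the treatment promising if at least 14 are without progression at 2 years from the end of treatment. It gives power of 0.99 at a true rate of 90% and type 1 error below 0.01 at 40%.

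**The concern.** Consider three patients who are alive and attend every clinic visit to month 24.

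- **A** has a clear scan at 24 months. Success, correctly.
- **B** was last scanned at 6 or 12 months. The patient is attending and nothing shows progression, so the literal wording gives a success, although 2-year status is unknown.
- **C** is like B but has in-field growth of more than 25% that a scan would have shown. The literal wording again gives a success, although Section 12 defines this as failure.

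A fourth patient, who stops attending, is scored as a failure. The plan therefore treats missing outcome conservatively when the patient is absent and favourably when only the scan is absent. In a single-arm trial with a fixed cut-off, the second treatment can only raise the success count, so it erodes the protection against a false positive claim. Leaving the point open also allows the scoring choice to be made after results are known.

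**Working it through.** **Inputs from Section 14.** n = 19; success if at least 14 are progression-free; null rate 0.40; target rate 0.90.

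**Assumed input.** k = number of patients alive and in follow-up but without 2-year imaging. The documents give no figure, so k runs from 0 to 5. The k patients are taken as unscanned for reasons unrelated to their true outcome.

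**Step 1: reproduce the plan's figures (k = 0).**
- P(Bin(19, 0.40) ≥ 14) = 0.0031, below the stated 0.01.
- P(Bin(19, 0.90) ≥ 14) = 0.9914, matching the stated 0.99.

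**Step 2: upper case.** Every unscanned patient is scored a success whatever happened, and the other 19 − k succeed at 40%. Type 1 error = P(Bin(19 − k, 0.40) ≥ 14 − k). For k = 2 this is P(Bin(17, 0.40) ≥ 12) = 0.0106.

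**Step 3: milder cases.** An unscanned patient had earlier scans, and progression seen on them already counts. Assume a constant hazard with 40% event-free at 24 months. A patient last scanned at month m is then scored a success with probability 0.40^(m/24): 0.503 for m = 18, 0.632 for m = 12 and 0.795 for m = 6. Type 1 error is the probability that the sum of Bin(k, 0.40^(m/24)) and Bin(19 − k, 0.40) is at least 14. This treats every event after the last scan as unseen. Deaths after that scan would still be scored as failures, so under this model the figures lean high.

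| k | Step 2: all scored success | Last scan 6 months | Last scan 12 months | Last scan 18 months |
|---|---|---|---|---|
| 0 | 0.0031 | 0.0031 | 0.0031 | 0.0031 |
| 1 | 0.0058 | 0.0048 | 0.0041 | 0.0035 |
| 2 | 0.0106 | 0.0075 | 0.0055 | 0.0041 |
| 3 | 0.0191 | 0.0116 | 0.0072 | 0.0046 |
| 4 | 0.0338 | 0.0177 | 0.0096 | 0.0053 |
| 5 | 0.0583 | 0.0266 | 0.0125 | 0.0061 |

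The stated bound of 0.01 is passed at k = 2 in the upper case, at k = 3 with last scans at 6 months and at k = 5 with last scans at 12 months. With last scans at 18 months it is not passed within the range.

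**Step 4: another way to size it.** Suppose a share u of true failures is missed for lack of a scan. The apparent success rate under the null is 0.40 + 0.60u. For u = 10% this is 0.46, and P(Bin(19, 0.46) ≥ 14) = 0.0137. The bound of 0.01 is passed at about u = 8%.

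**Step 5: cost of scoring unscanned patients as not progression-free.** Power = P(Bin(19 − k, 0.90) ≥ 14) = 0.972, 0.917, 0.789 and 0.549 for k = 1, 2, 3 and 4. Type 1 error stays at or below 0.0031.

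**The case against.** The strongest reply is that the plan does schedule the scans. Section 12 says they will be done through 2 years, and Section 10.2.2 repeats imaging on the same calendar. A patient without a 24-month scan is then a deviation, not something the plan permits. This stands, and it rules out the stronger reading that 2-year imaging is optional altogether. It does not settle how a missed scan is scored.

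A reader might also infer that any living patient without a neck CT or MRI becomes a success. The documents do not support that. Metabolic tumor volume and total lesion glycolysis are failure criteria in their own right, so a PET/CT can supply the assessment, and patients lost to follow-up are scored as progression. What remains unclear is whether PET/CT is required after 3 months.

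Next, loss to follow-up is undefined. For an imaging endpoint it could be read to cover an attending patient without imaging, and Section 13 allows removal for continual non-compliance with the follow-up schedule. This is a possible reading, so scoring such a patient as a success is the literal result of the default wording and not an explicit statement. If the sponsor means the other reading, the plan should say so.

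Finally, it is tempting to say that the type 1 error claim fails once two patients are unscanned. That is true only if both are certain successes. With last scans at 12 months and a constant hazard, two unscanned patients give 0.0055.

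**Conclusion.** The point holds as a gap in the scoring rule that leans toward success. Section 12's default and Section 14's short list of missing-data failures, read together, place an attending patient without 2-year imaging among the successes. The plan's stated figures are not wrong: both reproduce, on the condition that every 2-year status is known.

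The size depends on assumptions the documents cannot settle. With two to five unscanned patients, type 1 error runs from 0.0106 to 0.058 if all are scored as successes, and from 0.0055 to 0.0125 if they were scanned to 12 months under a constant hazard. Both ranges assume that a missing scan is unrelated to outcome; if scans were missed mainly in patients who had progressed, the error would be larger. The direction is certain, because the default cannot remove a success. It is a cheap improvement, not a fault that invalidates the design.

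**What to change.** In Sections 12 and 14:

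1. Count a patient as loco-regionally progression-free at 2 years only if alive with an imaging assessment (CT, MRI or FDG PET/CT) in the 24-month window, or on a later scan if one was done, that meets no failure criterion.
2. Score a patient without such imaging as not progression-free, in line with the existing rule for loss to follow-up, and define loss to follow-up.
3. Report the number of patients without 2-year imaging, with a sensitivity analysis that uses status at the last available scan.
4. Reconcile the late scan window, which is +/- 6 weeks in Sections 10.2.2 and 12 and +/- 8 weeks in table footnote d, and make the text and the schedule table agree on which imaging supplies the 2-year assessment.

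This takes a few sentences and no new procedure, since imaging is already scheduled to 2 years. The price is power: a truly controlled but unscanned patient now counts against the treatment, so at a 90% rate power falls from 0.991 to 0.972, 0.917 and 0.789 with one, two and three such patients. Accepting a later scan softens this only where one happens to be done, because the imaging schedule ends at 2 years. The sensitivity analysis shows how far the conclusion depends on the convention.
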